5.4. Rationale for the Current Study

The purpose of this study is to evaluate the ongoing safety and tolerability of additional treatment with eteplirsen, administered once weekly by IV infusion in male DMD patients who have successfully completed the 96-week eteplirsen study: Study 4658-102. This study also plans to evaluate the efficacy of additional treatment with eteplirsen administered once weekly by IV infusion in male DMD patients who successfully completed Study 4658-102.

5.5. Benefit and Risk Assessment

Details about the known and expected benefits and risks of, and expected AEs associated with, eteplirsen treatment are provided in the eteplirsen Investigator's Brochure.

Eteplirsen has been granted accelerated approval in the US by the Food and Drug Administration. This was based on the observation of dystrophin production in some patients and the safety experience in patients with DMD participating in clinical trials, who were 4 years of age or older, which includes the age range specified for this study. Patients have also used commercially available eteplirsen since the approval in September 2016.

To date, eteplirsen has been well tolerated, with low rates of serious or severe AEs. No major safety risk has been identified in patients dosed with eteplirsen, including patients dosed with up to 50 mg/kg once weekly for more than 4 years.

Risks with eteplirsen include infusion-related reactions, hypersensitivity reactions, and potential renal toxicities including proteinuria or decreased renal function. These events have been seen in prior experience with eteplirsen with lower doses and are usually mild and resolve without clinical or pharmaceutical treatment. The use of higher doses of eteplirsen in this protocol could lead to more frequent or more severe reactions than seen with lower doses. Regularly scheduled review by a Safety Review Committee during the open-label period and a Data Monitoring Committee (DMC) during the double-blind period will look at aggregate unblinded data to determine the relative risk-benefit of continuing the dose or the study. Investigators are allowed to withhold dosing and must discuss such actions with the Medical Monitor. Further details on the safety of eteplirsen can be found in the Investigator's Brochure.

Based on the mechanism of action of eteplirsen and the benefit of eteplirsen treatment in DMD patients with mutations amenable to skipping exon 51, it is expected that patients in Study 4658-102-OLE may derive a clinical benefit from treatment with a higher dose of eteplirsen.

Taken together, these considerations support that patients participating in Study 4658-102-OLE will not be exposed to undue risk and may potentially experience some clinical benefit.

6. STUDY OBJECTIVES AND PURPOSE

6.1. Primary Objective

- To evaluate the ongoing safety and tolerability of additional treatment with eteplirsen administered once weekly by IV infusion in male DMD patients who have successfully completed the 96-week eteplirsen study: Study 4658-102.

6.2. Exploratory Objective

- CCI

7. INVESTIGATIONAL PLAN

7.1. Overall Study Design

This is an open-label extension (OLE) study to assess the ongoing safety, tolerability, and efficacy of weekly IV infusions of eteplirsen in DMD patients who have successfully completed Study 4658-102.

Patients will have the opportunity to enroll in this study during the last visit of Study 4658-102 (Week 96). After enrollment, patients will receive the [REDACTED] mg/kg dose of eteplirsen while in this study. The period from Baseline through Week 284 will be considered the “Treatment Period.”

Week 284 will be followed by a 4-week Safety Follow-up Period. Patients may transition to commercially available product if commercially available eteplirsen is available at any time during the study, without undergoing the Safety Follow-up Period. Home infusion of the study drug may be available.

Safety and efficacy assessments will be performed at scheduled visits; AEs, concomitant medications, and concomitant therapies will be continuously monitored.

[REDACTED]

If review of data from this OLE study suggests that continued treatment with eteplirsen is warranted, this study may be extended by protocol amendment, or patients may transition to commercially available product if commercially available eteplirsen is available.

Refer to Section 10 for the detailed list of study assessments.

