1. SYNOPSIS

NAME OF COMPANY Sarepta Therapeutics, Inc. [name] [contact]	NAME OF FINISHED PRODUCT Eteplirsen Injection
	NAME OF ACTIVE INGREDIENT Eteplirsen
TITLE: An Open-Label Safety, Tolerability, and Efficacy Study of Eteplirsen in Patients with Duchenne Muscular Dystrophy Who Have Completed Study 4658-102	
Study Number: 4658-102-OLE	
Phase of Study: Phase 2	
INVESTIGATOR STUDY SITES: This multicenter study will be conducted at approximately 4 sites in Europe.	
OBJECTIVES: Primary Objective 
• To evaluate the ongoing safety and tolerability of additional treatment with eteplirsen administered once weekly by intravenous (IV) infusion in male Duchenne muscular dystrophy (DMD) patients who have successfully completed the 96-week eteplirsen study: Study 4658-102. Exploratory Objective 
• CCI	
METHODOLOGY: This is an open-label extension (OLE) study to assess the ongoing safety, tolerability, and efficacy of weekly IV infusions of eteplirsen in DMD patients who have successfully completed Study 4658-102. Patients will have the opportunity to enroll in this study during the last visit of Study 4658-102 (Week 96). After enrollment, patients will receive the CCI mg/kg dose of eteplirsen while in the study. The period from Baseline through Week 284 will be considered the “Treatment Period.” Week 284 will be followed by a 4-week Safety Follow-up Period. Patients may transition to commercially available product if commercially available eteplirsen is available at any time during the study, without undergoing the Safety Follow-up Period. Home infusion of the study drug may be available. Safety and efficacy assessments will be performed at scheduled visits; adverse events (AEs), concomitant medications, and concomitant therapies will be continuously monitored. The CCI (CCI) will be administered to all patients; a revised version will be used for patients \leq 3 years of age. If review of data from this OLE study suggests that continued treatment with eteplirsen is warranted, this study may be extended by protocol amendment, or patients may transition to commercially available product if commercially available eteplirsen is available.	
NUMBER OF PATIENTS: Up to 15 patients will be enrolled in this study.	

NAME OF COMPANY	NAME OF FINISHED PRODUCT
Sarepta Therapeutics, Inc. [name] [contact]	Eteplirsen Injection

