- d. Vital signs will include blood pressure, heart rate, respiration, and axillary temperature. On infusion days, vital signs will be measured within 60 minutes prior to infusion and 30 minutes (\pm 10 minutes) after the end of the infusion. All assessments will be performed after patients have remained calm for 5 minutes. Pulse rate and respiratory rate should be measured over 1 minute.
- e. Height and ulnar length will be measured as part of every physical examination. The examination will also include general appearance; head, ears, eyes, nose, throat; heart; lungs; chest; abdomen; skin; lymph nodes; musculoskeletal system; and neurological systems.
- f. Patients will receive ~~cc~~ mg/kg of eteplirsen once a week over 35-60 minutes, and will be observed for at least 1 hour after each infusion. It is recommended that a topical anesthetic cream (eg, lidocaine 2.5%, prilocaine 2.5%, or LMX4 cream) be applied to the injection site prior to each infusion.

Once a patient begins receiving weekly eteplirsen infusions at satellite sites, all subsequent infusions should be administered at the patient's satellite site unless otherwise indicated and approved by the Medical Monitor. Patients may receive home infusions starting at Week 1. Note that an implanted venous access port may be inserted for eteplirsen administration at the discretion of the Investigator.

- g. AEs should be recorded at all visits. Spontaneously reported AEs occurring within 28 days after the last dose of eteplirsen will also be recorded.
- h. In the event that a patient experiences an AESI of infusion-related reaction, an infusion-related reaction case report form should be completed.
- i. Special situations (eg, overdose, medication error, accidental/occupational exposure) should be monitored and recorded.
- j. For patients aged \leq 3 years the revised ~~CCI~~ will be used. For patients aged >3 age-appropriate items from the ~~CCI~~ (Mercuri 2016) should be performed.
- k. Patients who are withdrawn from the study early will be asked to complete all end-of-study (EOS) assessments prior to withdrawal and within 28 days of their last eteplirsen infusion, if possible, unless they have completed a physical exam and safety labs within 28 days of withdrawal.
- l. All patients will be asked to complete the Safety Follow-up visit 28 days after their last dose of eteplirsen. Patients may transition to commercially available product if commercially available eteplirsen is available.

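### The protocol both waives and requires Safety Follow-up for patients who move to commercial eteplirsen, so their adverse-event recording is tied to a visit that may not occur

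*Combined protocol and SAP*

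**What the plan says.** **Passages with the waiver.** Section 7.1 allows the move to commercial product if "commercially available eteplirsen is available at any time during the study, without undergoing the Safety Follow-up Period". The synopsis carries the same condition, that the product "is available at any time during the study, without undergoing the Safety Follow-up Period". Section 8.5 fits this: it lists transition as a way for the study to end, beside the 4-week follow-up to Week 288.

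**Passages without it.** Table 2 footnote l reads "All patients will be asked to complete the Safety Follow-up visit 28 days after their last dose of eteplirsen". Its next sentence is "Patients may transition to commercially available product if commercially available eteplirsen is available", which permits the move and waives nothing. Section 8.4 says the visit will take place about 4 weeks after the last dose, however long the patient was in the study. Section 10.3.8 monitors AEs up to each patient's Safety Follow-up visit, and Section 11.1 records AEs up to that visit. Section 9.2 describes a follow-up period of up to 4 weeks after Week 284 and permits transition, again with no waiver.

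**Analysis window.** Sections 11.2.1 and 13.7.1 count an AE as treatment-emergent up to 28 days, or 4 weeks, after the last dose of study drug.

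**Other capture rules.** Footnote g says "Spontaneously reported AEs occurring within 28 days after the last dose of eteplirsen will also be recorded". Section 11.1 adds that related serious events the site learns of after participation ends must be reported. Footnote k says "Patients who are withdrawn from the study early will be asked to complete all end-of-study (EOS) assessments", and Section 8.6 has a similar Early Termination rule for patients withdrawn from treatment.

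**The concern.** Safety and tolerability is the only primary objective, and at most 15 patients will be enrolled. For one exit route, the passages differ on whether the last safety visit takes place, and AE recording is defined by that visit. Two sites relying on different sections could stop recording at different points for patients who leave in the same way.

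The analysis applies the same 28-day window to everyone. For a patient who skipped the visit, an empty window in the tables could mean that nothing happened or that nobody asked. A patient who goes straight on to commercial eteplirsen may also receive commercial doses inside that window. An AE there would count as treatment-emergent to study drug with nothing to show that commercial dosing had begun.

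The protocol handles a comparable handover explicitly. The rollover note under Table 2 says when the main-study safety follow-up visit is and is not needed, using 7-day and 4-week limits. The move to commercial product has no equivalent.

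**Working it through.** The plan gives no figure to reproduce. The check sets the passages side by side and then bounds the size.

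**1. Is the visit waived?** Two places say yes (synopsis, Section 7.1), and Section 8.5 is consistent with them. Four places state the visit, or recording through it, without exception (footnote l, Sections 8.4, 10.3.8 and 11.1). Section 9.2 does not decide it. The lengths agree (28 / 7 = 4 weeks; Week 284 + 4 = Week 288), so the conflict is not about duration.

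**2. If the waiver governs, when does AE recording end?**
- Sections 10.3.8 and 11.1 end it at a visit that is not held.
- Section 11.4 records AEs to the last follow-up, which is not defined for these patients. It follows AEs until resolution, completion of participation or study termination, whichever comes first.
- Section 8.4 completes participation with the Week 284 assessments and measures its length to the Safety Follow-up visit. A patient who transitions before Week 284 and skips the visit reaches neither.

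**3. What capture clearly remains in the 28 days?**
- Spontaneous reports under footnote g. These are counted from the last dose of eteplirsen, which for these patients may be a commercial dose. The treatment-emergent definitions count from the last dose of study drug, so the two dates can differ.
- Related serious events the site becomes aware of (Section 11.1).
- Possibly the end-of-study or Early Termination assessments (footnote k, Section 8.6), if a patient who transitions counts as withdrawn. The text does not say.

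**4. Size.** Inputs from the documents: a 28-day window, at most 15 patients, and treatment to Week 284. Not in the documents, so assumed: how many patients transition and when.
- Per patient: 28 / 365.25 = 0.077 patient-years.
- Share of the treatment-emergent period = 28 / (exit week × 7 + 28), taking the last study dose at the exit week:
  - Week 284: 28 / 2016 = 1.4%
  - Week 144 (assumed): 28 / 1036 = 2.7%
  - Week 48 (assumed): 28 / 364 = 7.7%
- Total for 0, 1, 5 or 15 patients transitioning (assumed): 0, 0.08, 0.38 or 1.15 patient-years.
- Maximum observation if all 15 are followed to Week 288: 15 × 288 × 7 / 365.25 = 82.8 patient-years.

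These are upper bounds. Any spontaneous report or Early Termination visit reduces the gap.

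**The case against.** The strongest reply is that a site can follow all of these passages by treating the synopsis and Section 7.1 as a specific exception to a general rule. Section 8.5 supports that. Footnote l only says patients will be asked to attend, and its second sentence can be read as a shortened form of the exception. The Section 8.4 phrase about duration concerns time on study, not exit route. This largely stands for the visit itself. A reader might infer that sites cannot comply with both sets of passages, and the documents do not support that. The reply does not settle AE recording, because under the exception Sections 10.3.8 and 11.1 point to a visit that is not held.

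A second reply is that AE capture is not wholly open. The treatment-emergent window is clearly defined, footnote g does not depend on the visit, and Section 11.4 follows serious events to resolution, stabilisation or return to Baseline. The withdrawal reasons in Section 8.6 are not exhaustive, so its Early Termination rule may reach these patients. All of this is correct, and it is why the 28 days are an upper bound. But a defined window for classifying events does not say who collects them, and the Section 8.6 route depends on an unstated classification.

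A third reply is that few patients may ever transition. The synopsis says "This multicenter study will be conducted at approximately 4 sites in Europe", while the only approval mentioned is in Section 5.5: "Eteplirsen has been granted accelerated approval in the US by the Food and Drug Administration". That stands and limits the severity.

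**Conclusion.** Wrong as written: an internal contradiction of low to moderate severity. The waiver and the unqualified follow-up statements need reconciling. Even on the reading most favourable to the plan, AE collection for patients who transition is not clearly matched to the treatment-emergent window.

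The gap is at most 28 days (0.077 patient-years) per such patient. That is 1.4% of the treatment-emergent period for exit at Week 284, a larger share of a shorter period for earlier exit, and zero if nobody transitions. The bound assumes no capture at all in the window. The number and timing of transitions are not in the documents.

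A reader might go further and infer that crude AE percentages would be seriously distorted by early transition. That does not follow from this conflict. A patient leaving at Week 48 is observed for 48 weeks without the visit and 52 with it, against 288 for a patient followed to the end (ratios 288 / 48 = 6.0 and 288 / 52 = 5.5). Nearly all of the difference is treatment time, which no follow-up rule changes. Section 13.1 also leaves method details to an SAP that is not part of the text reviewed. Nor can it be said that transitions will go unreported, since Section 13.5 already summarises premature discontinuations with reasons.

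**What to change.** - Reconcile the synopsis and Sections 7.1 and 8.5 with Table 2 footnote l and Sections 8.4, 9.2, 10.3.8 and 11.1. Which follow-up rule applies is for the sponsor to decide.
- Under whichever rule is kept, state how and until what date AEs are collected for patients who transition, so that collection covers the existing 28-day treatment-emergent window.
- Say that the 28 days count from the last study dose, and align footnote g with that. Record the first commercial dose date so that AEs starting after it can be identified.
- State when participation ends for these patients, and whether footnote k and Section 8.6 apply to them.
- Optionally, show transition to commercial product as its own row in the Section 13.5 disposition summary.

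The cost is protocol wording and a small amount of extra AE and date collection per patient who transitions, plus one table row if the option is taken. The wording is best settled before anyone transitions, because AEs not asked about at the time may not be recoverable later.

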7.2. Dose Selection Rationale

Eteplirsen will be dosed weekly at [REDACTED] mg/kg over the course of 284 weeks, based upon the dosing scheme utilized in Study 4658-102.

Dose selection for the patient group aged 6 months to 4 years was based on the assumption that efficacy relates to exposure, defined using AUC. The [REDACTED] mg/kg dose was chosen as the target dose based on results from the Phase 2, double-blind, placebo-controlled, multiple-dose study, Study 4658-us-201, and its OLE study, Study 4658-us-202. As described in Section 5.3, these studies assessed the efficacy, safety, tolerability, and pharmacokinetics of 2 eteplirsen doses ([REDACTED] and [REDACTED] mg/kg) administered as IV infusions in 12 patients, aged 7 to 13 years, diagnosed with DMD with a deletion mutation amenable to exon 51 skipping.

As of 24 June 2019, 182 patients with DMD and 59 non-DMD subjects have been treated with eteplirsen in clinical studies, including 175 who received IV eteplirsen and 155 who received [REDACTED] mg/kg or higher. Of the 182 patients, 17 and 135 patients received at least 48 and 96 weeks of eteplirsen treatment, respectively. This includes 12 patients from Study 201/202 who have been treated for over 5 years. These studies demonstrated that treatment with eteplirsen was generally well-tolerated at doses of [REDACTED] mg/kg (N=149) and 50 mg/kg (N=6) and there were no observed difference in safety between these 2 doses.

In these studies, once-weekly treatment with [REDACTED] mg/kg eteplirsen for 24 weeks significantly increased the mean percentage of dystrophin-positive muscle fibers as percentage (%) of normal

in DMD patients compared to placebo. At Week 48, increases in the percentage of dystrophin-positive fibers were similar for patients who had received weekly 30 and 50 mg/kg eteplirsen doses from Week 1 (52% and 42% of normal, respectively, or 47% for the combined groups; data on file). These data suggest that the effect of eteplirsen on the production of novel dystrophin is not significantly different between the 2 doses tested. Therefore, the lower (cc) mg/kg dose was selected as the more conservative choice, because patients presumably would receive this drug as a lifelong treatment. To date, there is no evidence that the response differs across age groups.

The overall safety data obtained to date do not indicate any significant safety concerns with eteplirsen at doses that are one-third to one-half of the dose in this study. For patient exposure and safety data, please refer to the eteplirsen Investigator's Brochure.

7.3. Study Endpoints

7.3.1. Safety and Tolerability Endpoints

- Incidence of AEs, serious adverse events (SAEs), and discontinuation from treatment due to AEs
- Incidence of deaths due to AEs
- Incidence of adverse events of special interest (AESIs), including infusion-related reactions, hypersensitivity, and renal events
- Clinically significant laboratory testing, including hematology, coagulation, serum chemistry, and urinalysis
- Clinically significant cardiac function assessments, including electrocardiogram (ECG)
- Clinically significant vital signs
- Clinically significant physical examinations

7.3.2. Exploratory Endpoint

CCI

7.4. Discussion of Study Design

This OLE study focuses on safety and efficacy in male DMD patients who initiated eteplirsen treatment as early as 6 to 48 months of age. **CCI**

No other disease-modifying treatment exists to serve as an appropriate, active comparator for this patient population of boys with DMD aged 6 to 48 months; ataluren is commercially available in the European Union, but is not indicated for use in patients with exon 51-amenable mutations (PTC Therapeutics).

The patients in this study will have an established clinical diagnosis of DMD with a deletion mutation amenable to exon 51 skipping. These are the patients for whom eteplirsen is potentially effective and may result in slowing of disease progression. The age range for the patients in the original study (Study 4658-102) (6 to 48 months old, inclusive) was chosen to establish the safety profile of eteplirsen in this age group.

Patients will have the option to continue to receive once-weekly IV infusions of eteplirsen for up to 284 weeks, in order to obtain safety data in this population. Refer to the eteplirsen Investigator's Brochure for safety information.

8. SELECTION AND WITHDRAWAL OF SUBJECTS

8.1. Number of Patients

Up to 15 patients will be enrolled in this study.

8.2. Patient Inclusion Criteria

A patient must meet all of the following criteria to be eligible to participate in this study:

1. Patient has successfully completed 96 weeks of treatment in Study 4658-102.
2. Parent(s) or legal guardian(s) who is/are able to understand and comply with the study requirements.
3. Patient and/or their parent(s)/legal guardian(s) are willing and able to provide signed informed consent.

8.3. Patient Exclusion Criteria

A patient who meets the following criterion will be excluded from this study:

1. Patient has a prior or ongoing medical condition that, in the Investigator's opinion, could adversely affect the safety of the patient, or make it unlikely that the course of treatment or follow-up would be completed, or impair the assessment of study results.

